8.3.2. Physical Examinations

Physical examinations must be performed by a medically qualified individual, such as a licensed physician, a physician assistant, or an advanced registered nurse practitioner, as local law permits. Abnormalities identified after the dose of study treatment constitute an AE if they are considered clinically meaningful, induce clinical signs or symptoms, or require concomitant therapy. Investigators should pay special attention to clinical signs related to previous serious illnesses.

At admission (Day -1) and on the day of discharge or ET, a comprehensive physical examination should be conducted (see Table 3). The comprehensive physical examination will include assessment(s) of the following organ or body systems: skin; head, eyes, ears, nose, and throat; thyroid; lungs; cardiovascular system; abdomen (liver, spleen); extremities; and lymph nodes; as well as a brief neurological examination that will include assessments of the central nervous system, peripheral nervous system, and cerebellar function.

A targeted physical examination may be conducted at any time at the investigator's discretion. Participants will be assessed by the investigator or medically qualified designee per institutional standard of care. These assessments should be an evaluation as indicated by participant symptoms, AEs, or other findings and documented on the Adverse Events Form in the eCRF.

Height will be assessed at screening. Body weight will be assessed and BMI will be calculated at both screening and admission.

8.3.3. Vital Signs

Vital sign measurements (to be taken before blood collection for laboratory and PK tests, except during screening) include blood pressure, pulse, respiratory rate, and body temperature. See Table 3 for the timing and frequency. Blood pressure and pulse will be taken with the participant in the supine position after 5 minutes of rest. All measurements will be performed singly and repeated once (within 15 minutes) if outside the relevant clinical reference range. Abnormal vital sign results identified after the dose of study treatment constitute an AE if they are considered clinically meaningful, induce clinical signs or symptoms, or require concomitant therapy.

8.3.4. Electrocardiograms

Single, 12-lead ECGs will be obtained as outlined in [Table 3](#) (to be taken before blood collection for laboratory and PK tests, except during screening) using an ECG machine that automatically calculates the heart rate and measures PR, RR, QRS, QT, and QTcF intervals. All 12-lead ECGs will be performed with the participant in a supine position after 5 minutes of rest.

The 12-lead ECGs will be interpreted by the investigator at the site to be used for immediate participant management. Single, 12-lead ECGs will be repeated once if the investigator deems a repeat is indicated. Additional 12-lead ECGs may be performed as clinically indicated to manage participant safety. The decision to include or exclude a participant based on an ECG flagged as "Abnormal, Clinically Significant" is the responsibility of the investigator, in consultation with the sponsor's medical monitor, as appropriate. Clinically notable abnormalities that are considered clinically significant in the judgment of the investigator are to be reported as AEs. The predose ECG will serve as baseline for the purposes of calculating change-from-baseline intervals.

8.3.5. Laboratory Assessments

See [Appendix B](#) for the list of clinical laboratory tests to be performed and [Table 3](#) for the timing and frequency. Scheduled chemistry and hematology samples will be taken following an 8-hour fast. A certified laboratory local to the investigative site will perform all clinical blood laboratory assessments for safety (ie, serum chemistries, hematology and serology assessments, and thyroid panel). Urinalysis will be performed on site by a trained clinical staff member using a dipstick. If urine microscopy or microbiology is required, samples will be sent to a certified laboratory local to the investigative site. Additional testing may be required by the sponsor based on emerging safety data. Additional tests may also be performed if clinically indicated. All Protocol-required laboratory assessments must be conducted in accordance with the CSPM and the SoA (see [Table 3](#)). Information regarding collection, processing, and shipping of laboratory samples will be provided to the site in the CSPM.

Clinically significant abnormal laboratory findings are those that are not associated with an underlying disease, unless judged by the investigator to be more severe than expected for the participant's condition. All laboratory tests with values considered clinically significantly abnormal during participation in the study or within 14 days after the dose of study treatment should be repeated until the values return to normal or baseline or are no longer considered clinically significant by the investigator or medical monitor.

Screening laboratory assessments must be performed within 28 days before Day 1. If laboratory samples are collected on Day 1, they must be performed before study treatment administration.

See Section [9.1](#) for information regarding laboratory abnormalities that should be recorded as an AE in the eCRF. Additionally, if laboratory values from laboratory assessments performed at the institution's local laboratory require a change in participant management (eg, require treatment) or are considered clinically significant by the investigator (eg, SAE or AE), then the result(s) of the specific laboratory assessment(s) must be recorded in the eCRF.

8.3.5.1. Serology

Hepatitis and HIV screening assessments will be performed at the screening visit to rule out infection; required analytes are shown in [Appendix B](#). Generally, hepatitis tests should be performed early in the screening process due to the length of time needed to obtain the results. Additional tests may be performed if clinically indicated.

8.4. Pharmacokinetic Assessments

8.4.1. Blood Sample Collection

All scheduled sample collection timepoints are relative to INCB099280 tablet administration. Blood samples will be collected for the determination of total radioactivity in whole blood and plasma. Plasma INCB099280 concentrations will also be determined using a validated bioanalytical method. Timing of blood PK sample collections is outlined in [Table 6](#). A maximum of 3 samples for determination of total radioactivity and 3 samples for metabolite profiling may be collected per participant at additional timepoints during the study if warranted and agreed upon between the investigator and the sponsor.

Sample collection, processing, storage, and shipping instructions will be provided in the Sample Management Instructions.

The participant's dose date and time associated with the serial blood and plasma sampling will be recorded on source documents and in the eCRF. The actual date and time (24-hour clock time) of each sample will be recorded. Missed, lost, or damaged samples must be recorded on the source documents and as a comment in the participant's eCRF.

After the predose PK sample is drawn, participants will begin the study treatment. Predose is defined as within 90 minutes before administration of study treatment.

Table 6: Pharmacokinetic Blood Sample Timing

| Sample Type | Pharmacokinetic Sample Collection Day | | | | | | |
|--|---|----------------------|---------------|---------------|---------------|----------------|-----------------------|
| | Day 1 | Day 2 | Day 3 | Day 4 | Day 5 | Day 6 | Day 7-12 ^a |
| Plasma INCB099280 concentrations | 0 h (predose) and 0.5, 1, 2, 4, 6, 8, 12, and 16 h postdose | 24 and 36 h postdose | 48 h postdose | 72 h postdose | 96 h postdose | 120 h postdose | Not required |
| Total radioactivity (plasma and blood) | 0 h (predose) and 0.5, 1, 2, 4, 6, 8, 12, and 16 h postdose | 24 and 36 h postdose | 48 h postdose | 72 h postdose | 96 h postdose | 120 h postdose | Q24H until discharge |
| Metabolite profiling | 0 h (predose) and 1, 2, 4, 8, 12, and 16 h postdose | 24 and 36 h postdose | 48 h postdose | 72 h postdose | 96 h postdose | 120 h postdose | Q24H until discharge |

Note 1: Participants withdrawn from the study prematurely will have PK samples collected at ET.

Note 2: PK windows will be listed in the eCRF clinical guidelines.

^a As needed.

8.4.2. Urine Sample Collection

Urine samples will be collected over the following intervals in relation to INCB099280 tablet administration: -12 to 0 hours (predose void [spot sample only]); 0 to 6, 6 to 12, and 12 to 24 hours postdose; and continuing in 24-hour intervals until the participant is discharged from the CRU. If a urine sample is not provided, it will not be considered a deviation. Total radioactivity analysis of urine samples will occur until study discharge criteria are met. Urine collections will be used to assess the excretion of total radioactivity and for metabolite profiling. Urine INCB099280 concentrations will also be determined using a validated bioanalytical method. Processing, storage, and shipping instructions for these urine samples will be provided in the Sample Management Instructions. Missed samples, spillage, or other loss of sample that results in incomplete urine collection must be recorded on the study source documents and as a comment in the eCRF.

8.4.3. Fecal Sample Collection

Fecal samples for total radioactivity analysis and metabolite profiling will be collected at the following time intervals in relation to INCB099280 tablet administration: -12 to 0 hours (predose [spot sample only]; whenever possible), 0 to 24 hours postdose, and continuing in 24-hour intervals until CRU discharge). If a predose fecal sample cannot be obtained, the participant will still be administered study treatment. If a sample is not provided, it will not be considered a deviation. Total radioactivity analysis of fecal samples will occur until study discharge criteria are met. Processing, storage, and shipping instructions for these fecal samples will be provided in the Sample Management Instructions.

8.4.4. Emesis Sample Collection

For participants with emesis within 4 hours after dose administration, vomitus will be collected and stored for possible radioactivity analysis. The time and date of collection will be recorded on the participant's source documents and in the eCRF. Vomitus will be analyzed as deemed appropriate. The sponsor will decide whether the participant should be replaced.

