2.1.4.1. Clinical Pharmacology

INCB 99280-101 is a completed study in healthy participants. After single-dose treatment of 25, 75, or 150 mg under fasting conditions, INCB099280 attained peak plasma concentration at approximately 4 hours (ranging from 1 to 6 hours) and then was eliminated in a multiphasic manner. The mean PK exposures after a single dose of 150 mg seemed to increase proportionally

as dose increased from 75 to 150 mg, whereas such exposures appeared to increase supraproportionally as dose increased from 25 to 75 mg. The geometric means of the $t_{1/2}$ were between 10 and 12 hours across the 3 single-dose levels studied, with up to 20% GCV, suggesting the dose supraproportionality between 25 and 75 mg was likely attributable to drug absorption rather than elimination. The interindividual variabilities were 91% GCV in C_{max} and 75% GCV in $AUC_{0-\infty}$ for the dose level of 150 mg but were moderate (39% to 70% GCV) for lower dose levels. There was a minimal extent of renal excretion.

After a high-fat meal and following a single dose of INCB099280 150 mg, the plasma exposures (C_{max} and $AUC_{0-\infty}$) of INCB099280 were 57% and 43% lower, respectively, than under the fasting condition in 12 healthy participants. The time to peak concentration was significantly longer than under fasting conditions, with the median t_{max} changed from 4 to 6 hours. The $t_{1/2}$ was estimated as 15 to 16 hours, not different between fasting and fed states. After a medium-fat meal and following a single dose of INCB099280 150 mg, the plasma exposures (C_{max} and $AUC_{0-\infty}$) of INCB099280 were 36% and 26% lower, respectively, than under the fasting condition in 12 healthy participants. The time to peak concentration under fed status was significantly longer than under fasting, with the median t_{max} changed from 4 to 7 hours. The means of estimated $t_{1/2}$ were approximately 12 to 13 hours, not different between fasting and fed states.

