4. STUDY DESIGN

4.1. Overall Design

This is a Phase 1, single-center, open-label, mass balance study of [¹⁴C]INCB099280. Study treatment will consist of a single dose of INCB099280 400 mg administered in tablet form (4 × 100-mg tablets) with 240 mL of water followed approximately 10 minutes later by an oral dose solution containing [REDACTED] of [¹⁴C]INCB099280 (not more than [REDACTED]
[REDACTED]

Healthy male participants will receive study treatment on Day 1 after an overnight fast of at least 8 hours, with food intake allowed no sooner than 4 hours postdose. In addition, except for the water provided for dose administration, water will be restricted for 1 hour before INCB099280 tablet administration until 1 hour postdose.

Participants will be admitted to the CRU on Day –1 at a time determined by the clinic. Participants will remain in the CRU until at least Day 6, but potentially up to Day 12, based on satisfying both of the following discharge criteria:

- $\geq 90\%$ of the administered radioactive dose is recovered in excreta (urine and feces combined).
- $< 1\%$ of the administered radioactive dose is recovered in excreta (urine and feces combined) in 2 consecutive, 24-hour, urine and fecal samples in which both samples are provided.

If the discharge criteria are not met, then participants will be discharged no later than Day 12 (264 hours postdose on the morning of Day 12).

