8.4.5. Bioanalytical Methodology and Sample Analysis

Pharmacokinetic blood samples will be centrifuged, and plasma will be harvested for bioanalysis. The plasma samples will be analyzed for INCB099280 using a validated bioanalytical method. Blood, plasma, urine, feces, and vomitus (if applicable) total radioactivity will be determined with liquid scintillation counting.

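### Vomitus collection is planned only for the first 4 hours and its analysis is optional, so label vomited later would be an unmeasured gap in one participant's recovery

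*Combined protocol and SAP*

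**What the plan says.** Section 8.4.4 sets the rule: "For participants with emesis within 4 hours after dose administration, vomitus will be collected and stored for possible radioactivity analysis". The date and time of each sample are recorded. Analysis is discretionary ("Vomitus will be analyzed as deemed appropriate"), and so is what happens to the participant: "The sponsor will decide whether the participant should be replaced". Section 8.4.5 names the assay: "Blood, plasma, urine, feces, and vomitus (if applicable) total radioactivity will be determined with liquid scintillation counting". No other section plans vomitus collection after 4 h. Section 8.4.4 also does not say whether the clock starts at the tablets or at the labelled solution, which follows about 10 minutes later. Section 8.4.1 ties scheduled samples to the tablets, but emesis is not a scheduled sample.

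The surrounding text bears on the choice of 4 h:

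- **Absorption.** In the healthy-participant study at 25, 75 and 150 mg fasted, Section 2.1.4.1 reports that "INCB099280 attained peak plasma concentration at approximately 4 hours (ranging from 1 to 6 hours" across participants.
- **First food.** Section 4.1 doses after an overnight fast, "with food intake allowed no sooner than 4 hours postdose".
- **Other excreta.** Sections 8.4.2 and 8.4.3 run urine and fecal collection to discharge, which is Day 6 at the earliest and Day 12 at the latest.
- **Primary endpoint.** Section 3 and Section 10.4.2 define mass balance as urine plus feces. Vomitus has no term in the sum, whenever it is collected.

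**The concern.** Emesis is the only planned excreta collection with an early cutoff. The cutoff falls at about the typical fasted tmax, 2 h before the upper end of the tmax range, and when eating may begin. The protocol gives no reason for 4 h. It otherwise takes care over completeness: Section 5.3.3 bars showers for 24 h so that no sample is lost.

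What is at stake is how one participant's primary result can be read. Label vomited at, say, 5 h leaves the body outside urine and feces, so recovery reads low. The AE record would show that emesis occurred but not how much label it removed. The shortfall could then be emesis, retention or missed collections, in unknown proportions. Two of the protocol's own decisions would be taken without that figure. One is the sponsor's decision on replacement. The other is release before Day 12, which requires at least 90% of the dose in urine and feces and is out of reach after a loss of more than 10%.

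**Working it through.** The documents give no figure to reproduce: the 4 h window is a procedural choice and the sample size has no power calculation. The check sets the timings side by side and then sizes the possible loss.

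**Timings.** Window end 4 h; approximate fasted tmax 4 h, range 1 to 6 h; earliest food 4 h; urine and fecal collection to discharge.

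**Unabsorbed share at 4 h (illustrative).** Assume one compartment with first-order absorption.

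- Inputs: tmax 4 or 6 h, and half-life 10, 12 or 16 h. Section 2.1.4.1 says that geometric mean half-lives "were between 10 and 12 hours across the 3 single-dose levels studied", and gives 15 to 16 h in one of its food-effect comparisons.
- Elimination rate: ke = ln 2 / half-life.
- Absorption rate ka: solve tmax = ln(ka/ke) / (ka − ke).
- Share of the absorbable dose not yet absorbed at time t: exp(−ka·t).

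| tmax | half-life | ka (per h) | unabsorbed at 4 h |
|---|---|---|---|
| 4 h | 10 h | 0.615 | 8.5% |
| 4 h | 12 h | 0.671 | 6.8% |
| 4 h | 16 h | 0.759 | 4.8% |
| 6 h | 10 h | 0.329 | 26.8% |
| 6 h | 12 h | 0.365 | 23.2% |
| 6 h | 16 h | 0.423 | 18.4% |

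With tmax of 1 to 2 h the share is about 0.1% or less. In the slowest case (tmax 6 h, half-life 10 h), the share at 12 h is exp(−0.329 × 12) = 1.9%, and at 24 h it is exp(−0.329 × 24) = 0.04%.

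**Effect on recovery.** A loss of 10% of the dose lowers that participant's recovery by 10 points, to at most 90%, and lowers a six-participant mean by 10/6 = 1.7 points. A loss of 20% lowers the mean by 20/6 = 3.3 points.

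**Frequency.** Section 2.2 reports 1 drug-related vomiting event on the first day among 172 patients. The chance of at least one among n participants is 1 − (171/172)^n, which is 3.4% for n = 6 and 4.0% for n = 7. Even with a 20-point loss every time, the expected shift in mean recovery is 20 × 1/172 = 0.12 points.

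**What a longer window alone would do.** The Section 10.4.2 sum contains only urine and feces, so extending collection changes the reported mass balance by 0 unless the reporting also changes.

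**The case against.** The strongest case against is that the window is not what keeps vomited label out of the primary result. A reader might infer that a longer window would repair the mass balance. It would not: vomitus collected at 1 h has no place in the sum either, and even its analysis is optional. This stands, and it is why the fix must reach Section 10.4.2. It does not remove the point, because a sample that was never kept cannot be counted under any reporting rule.

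The size is also weakly supported, and that stands too:

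- A reader might take 4 h as the peak of absorption. Tmax is the peak of plasma concentration, where input equals elimination. Under first-order input the absorption rate is highest at the start, and 73% to 95% of the absorbable dose is already absorbed by 4 h.
- The modelled shares are not an upper bound. They leave out label that would never be absorbed, and they treat all unabsorbed drug as if it could be vomited. These errors run in opposite directions.
- The tmax data are for 25 to 150 mg. None is given for 400 mg or for the solution, which carries the label.
- The 22.7% vomiting rate in Section 2.1.4 comes from patients with advanced tumors, whose median exposure was 57 days (Section 2.2). It says little about the hours after one dose in healthy men. Among 76 healthy single-dose participants, vomiting is not listed among events seen in more than one, although those doses were lower.

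Finally, nothing forbids later collection, and participants are under daily AE assessment while confined. Late emesis would therefore be known, and a low recovery could be linked to it. What would be missing is the amount.

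**Conclusion.** The point holds as a minor but real gap. Collection of vomitus after 4 h is not planned and analysis before 4 h is not required, so a later loss would go unmeasured in the participant affected. It does not show that vomited label is irrecoverable, nor that the primary mass balance as a whole is at risk.

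The chance of any drug-related Day 1 vomiting is about 3% to 4% for 6 to 7 participants, and only part of that would fall after 4 h. This assumes that the patient rate of 1/172 carries over to healthy men; vomiting judged unrelated to the drug is not counted. The loss per event is uncertain: about 5% to 27% of the absorbable dose is still unabsorbed at 4 h under the first-order model with tmax of 4 to 6 h, and almost none if the labelled solution is absorbed faster. The expected effect on mean recovery is about 0.1 point, so the case rests on interpreting one participant out of six and on the low cost of the change.

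**What to change.** In Section 8.4.4, collect, time-stamp and weigh all vomitus throughout confinement. The minimum should be 24 h postdose, since under 0.1% of the absorbable dose remains unabsorbed by then in the slowest modelled case. Replace the discretionary wording with radioactivity counting of every sample. State whether time zero is the tablets or the solution.

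In Section 10.4.2, report the percentage of dose in vomitus separately, beside urinary and fecal recovery. For any participant with emesis, show urine-plus-feces recovery in two ways: as a percentage of the administered dose, and as a percentage of the dose net of measured vomitus. For example, if 10% is vomited and measured and everything else is recovered, the two figures are 90/100 = 90% and 90/(100 − 10) = 100%. The second figure is supportive and depends on how completely the vomitus was captured. The primary endpoint definition stays as it is.

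The cost is a few sentences and, only if emesis occurs, a few extra scintillation counts. Confinement and the assay are already in the protocol.

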8.4.5. Bioanalytical Methodology and Sample Analysis

Pharmacokinetic blood samples will be centrifuged, and plasma will be harvested for bioanalysis. The plasma samples will be analyzed for INCB099280 using a validated bioanalytical method. Blood, plasma, urine, feces, and vomitus (if applicable) total radioactivity will be determined with liquid scintillation counting.

8.4.6. Pharmacokinetic Analysis

Standard noncompartmental PK methods will be used to analyze the plasma and blood total radioactivity and plasma INCB099280 concentration data using Phoenix WinNonlin v8.0 or higher (Certara, Princeton, NJ). The actual times of postdose sample collections will be used. Predose PK samples will be assigned Time 0.

The PK parameters to be calculated for each matrix and analyte are presented in [Table 7](#).

Metabolite-to-parent compound (INCB099280) molar ratio of C_{\max} and AUC (AUC_{0-t}, AUC_{0-∞}, when available) will be calculated if metabolites are measurable. The linear trapezoidal rule for increasing concentrations and the log trapezoidal rule for decreasing concentrations will be used to calculate AUC_{0-t}. The AUC_{0-∞} will be calculated as AUC_{0-t} + C_t / λ_z .

Table 7: Pharmacokinetic Parameters

| Matrix and Analyte | Parameters |
|--|---|
| Whole blood and plasma total radioactivity | C_{\max} , t_{\max} , AUC _{0-t} , AUC _{0-∞} , $t_{1/2}$, CL/F, and V_z/F |
| Plasma INCB099280 concentration | C_{\max} , t_{\max} , AUC _{0-t} , AUC _{0-∞} , $t_{1/2}$, CL/F, and V_z/F |
| Urine INCB099280 concentration | A_e , f_e , and CL _R |

